### **12.5.2. Renal Events: Monitoring, Evaluation, and Discontinuation Criteria**

There are multiple potential reasons that sCr can increase in those with PNH, including hemolysis. For subjects who have a confirmed treatment-emergent increase in sCr, evaluations to investigate potential etiology should be chosen considering baseline renal function, history of prior renal events including those due to PNH, other comorbidities, concomitant medications, and other relevant factors. In addition, the following recommendations are made:

CCI

### **12.5.3. Risk of Hemolysis After Missed Doses, Treatment Interruption, or Permanent Discontinuation**

Investigators should remind subjects of the potential risk of hemolysis following missed doses (particularly multiple consecutive missed doses) and treatment interruption, and the definite risk after permanent discontinuation of BCX9930. By inhibiting the AP of complement, BCX9930 may improve Hb levels and increase circulating RBC clone size by reducing the hemolysis of PNH RBCs. Missed doses and treatment interruption of BCX9930 may lead to hemolysis. Subjects are at risk of severe hemolysis when BCX9930 is permanently discontinued. Based on available data regarding the PK and PD of BCX9930, severe hemolysis, if it occurs, would be expected to present within days after discontinuation of therapy.

Monitoring for hemolysis should be performed based on the medical judgement of the investigator. However, when subjects permanently discontinue BCX9930 at any time during the study, the following recommendations are made:

- If the subject is asymptomatic, it is recommended that contact with the subject be maintained on a daily basis for a minimum of 7 days. Contact may be conducted by telephone, email, or other means, including in person, if preferred. When any sign or symptom of hemolysis occurs, the subject should be promptly evaluated. Additional monitoring following the first contact after permanent discontinuation should be guided by the medical judgement of the investigator.

- For subjects who are already symptomatic when treatment is discontinued, whether the subject should be assessed in person or can be followed with daily contact will be based on the investigator's medical judgement taking into account the severity of the reported signs or symptoms and/or any reported worsening of the signs or symptoms. When possible, subjects should return to the investigative center; however, when this is not possible, arrangements may be made for the subject to be assessed by his or her local hematologist and a local laboratory used for clinical laboratory testing. When hemolysis occurs after the permanent discontinuation of BCX9930, treatment should be provided according to the judgement of the investigator.
- Subjects should be asked to contact the investigator if they experience any new or worsening signs or symptoms of hemolysis. Subjects should be evaluated per the investigator's medical judgement. A review of dosing compliance to ensure that the subject is taking the drug should be performed, regardless of the method used to evaluate the subject (ie, in-person or remote assessment). It should also be determined whether the subject has had any recent complement-activating conditions (eg, infection, trauma, or surgery) that may have contributed to the hemolytic event.
- Treatment with BCX9930 should not be interrupted or withheld unless there is an absolute contraindication for continued dosing. Suggestions for anti-emetic therapy for subject with active nausea and vomiting when tablet contents are vomited are given in Section [9.6.2](#).

The sponsor medical monitor should be notified in the event of hemolysis symptoms, any planned treatment interruption, or permanent discontinuation of BCX9930. Any missed doses, treatment interruption, or permanent discontinuation must be recorded in the eCRF and source documents, including the reason for the interruption, missed doses, or discontinuation.

## 12.6. Overdose

To date, there is no experience with overdose of BCX9930. Healthy subjects received BCX9930 at a dose of 2000 mg administered as single doses and as multiple once-daily doses for 3 days in Study 101 with no clinically significant safety concerns. If study personnel become aware of an overdose of BCX9930 that is associated with an AE, both the overdose and the resultant event should be reported as AEs. Overdose without any symptoms (ie, AEs) does not need to be reported as an AE. If overdose occurs with or without associated AEs, subjects should undergo clinical and laboratory monitoring, as appropriate, for their clinical condition and, if indicated, should receive clinically indicated supportive therapy. See also Section [12.1.2](#).

## 12.7. Data Monitoring Committees

A DMC has been established for ongoing safety monitoring. The specific responsibilities and composition of the DMC are outlined in a separate DMC charter. In addition, the details of outputs provided for the meetings will be referenced in this charter.

CCI

CCI

CCI

## 13. STATISTICS

### 13.1. Sample Size Considerations

No sample size calculations were conducted for this open-label, long-term safety study. Up to 30 subjects may be enrolled in this study, to allow continued access to BCX9930 following a subject's participation in another BCX9930 study.

### 13.2. Stratification

Not applicable.

### 13.3. Statistical Methods

A detailed statistical analysis plan (SAP) will be developed to describe the methods of analyses and summaries, including all endpoints, time points, populations, missing data, etc. Deviations from the analyses outlined in the SAP will be described in the clinical study report.

#### 13.3.1. Analysis Populations

The analysis populations for the study are defined below.

##### 13.3.1.1. Safety Population

The safety population is defined as all subjects who receive at least 1 dose of study drug. This population will be used for all analyses of accountability, demographics, and safety.

#### 13.3.2. General Considerations for Data Analysis

In general, descriptive summaries will include the sample size (n), mean, standard deviation (SD) and/or standard error (SE), median, minimum, and maximum for continuous variables and n and percentage for categorical variables. Data will be summarized by prior study and overall. Summaries will be presented by study visit where appropriate (eg, laboratory data) until subjects complete or withdraw from the study. No missing value imputation will be done. No statistical testing is anticipated as there are no a priori hypotheses stated for this study.

All individual subject data will be listed as measured. All statistical summaries and analyses will be performed using SAS® software (SAS Institute, Cary, North Carolina, USA), using version 9.4 or higher.

#### 13.3.3. Subject Demographic and Disposition Data

Demographic data and baseline characteristics including age, gender, race or ethnicity, height, body weight, BMI, and PNH history will be summarized by prior study and overall.

Subject disposition will be presented for all subjects and by prior study. The number of subjects who completed the study and those that discontinued from the study will be provided. The reasons for early discontinuation will be presented. A tabulation of the number of subjects exposed to study drug and duration of exposure will also be presented. Treatment adherence, dose interruptions, and reason for dose interruptions will be provided as summaries or listed, as appropriate.

### 13.3.4. Analysis of Safety Variables

Safety endpoints will be summarized and will include, at a minimum, the proportion of subjects 1) with TEAEs; 2) who discontinue due to a TEAE; 3) with treatment-emergent SAE; 4) with a Grade 3 or 4 TEAE; and 5) with Grade 3 or 4 laboratory abnormalities.

AEs will be mapped to a Medical Dictionary for Regulatory Activities (MedDRA, Version 24.0) preferred term and system organ classification. The occurrence of TEAEs will be summarized using MedDRA preferred terms, system organ classifications, and severity. In addition to severity, AEs and SAEs will also be summarized based on investigator assessment of relationship to study drug.

For all analyses of change from baseline, the baseline is the baseline value for the current study.

Descriptive statistics for vital signs, weight, and clinical laboratory results will be presented by study visit. Laboratory abnormalities will be graded according to CTCAE scales (Version 5.0, 27 November 2017). The number and percentage of subjects experiencing treatment-emergent graded laboratory toxicities will be summarized. Laboratory toxicity shifts from baseline to the worst post-baseline value as well as to the last visit will be summarized.

The number and percentage of subjects having elevations in ALT, AST, or bilirubin abnormalities in relation to fold above ULN will be summarized according to the US FDA's Premarketing Clinical Evaluation on Drug-Induced Liver Injury Guidance for Industry ([FDA 2009](#)).

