### 6.2. Endpoints

The endpoints of this study are:

- Subject incidence of graded TEAEs, laboratory abnormalities, changes to vital signs, and physical examination findings

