### 2.2. Endpoints

The endpoints of this study are:

- Subject incidence of graded treatment-emergent adverse events (TEAEs) and laboratory abnormalities.

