### **8.1. Overall Summary of Treatment-emergent Adverse Events**

The overall summary of TEAEs table for all subjects in the safety population will summarize the number and percentage of subjects that report at least 1 TEAE, have a treatment-related TEAE, have a TEAE leading to treatment withdrawal, have a serious TEAE requiring concomitant medication, have a severe (Grade 3) or life-threatening (Grade 4) TEAE, have a serious TEAE, have a TEAE leading to study discontinuation, and have a TEAE leading to death. In addition to summarizing the number and percentage of subjects that have at least 1 of these events, the table will also summarize the total number and percentage for each of these events. Results will be summarized for the BCX9930 400 mg BID, dose taper and Total. The percentages for number of subjects will use the safety population sample size as the denominator; the percentages for the number of events will use the total number of TEAEs as the denominator.

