### **8.2. Adverse Event Preferred Term and Body/Organ System Summary Tables**

#### **8.2.1. Treatment-emergent Adverse Events by System Organ Class and Preferred Term**

A summary of the number and percentage of subjects with treatment-emergent adverse events by system organ class and preferred term will be presented along with the number of events for all subjects in the safety population. Results will be summarized for the BCX9930 400 mg BID, dose taper and Total. The percentages for number of subjects will use the safety population sample size as the denominator.

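### The SAP only partly delivers the protocol's TEAE summaries by severity and relationship: no SOC/PT table shows grade, Grades 1 and 2 are not tabulated, and no table gives relationship for serious TEAEs

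*Protocol*

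**What the plan says.** **Endpoint.** Protocol Section 6.2 gives it as "Subject incidence of graded TEAEs, laboratory abnormalities, changes to vital signs, and physical examination findings". SAP Section 2.2 shortens it to "Subject incidence of graded treatment-emergent adverse events (TEAEs) and laboratory abnormalities". Vital signs and physical examination are dropped there, but the word graded is kept.

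**Promised analysis.** Protocol Section 13.3.4 first lists minimum safety summaries, among them the proportion of subjects with a Grade 3 or 4 TEAE. A separate paragraph then states: "The occurrence of TEAEs will be summarized using MedDRA preferred terms, system organ classifications, and severity". The next sentence goes beyond severity: "AEs and SAEs will also be summarized based on investigator assessment of relationship to study drug".

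**Planned analysis.** SAP Section 8.1 describes the overall table (14.3.1.1). It counts subjects who "report at least 1 TEAE, have a treatment-related TEAE, have a TEAE leading to treatment withdrawal", and also those who "have a severe (Grade 3) or life-threatening (Grade 4) TEAE, have a serious TEAE, have a TEAE leading to study discontinuation", together with TEAEs leading to death. The main table at term level, in SAP Section 8.2.1, is described this way: "A summary of the number and percentage of subjects with treatment-emergent adverse events by system organ class and preferred term will be presented". The serious, non-serious, renal and hepatic tables in SAP Section 8.2.2 follow the same pattern.

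**Declared changes.** SAP Section 9 limits summaries and listings to variables that matter for the abbreviated report. It does not mention severity or relationship.

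**The concern.** Safety monitoring is the only objective of this study that is measured with data, and its endpoint is defined by grade. With the planned tables, a reader learns how many subjects had any Grade 3 or 4 TEAE but not which events those were. The reader learns which terms were serious but not whether the investigator thought any serious event was related to the drug.

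Two features of the plan add to this.

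- SAP Section 5.7.2 sets a missing severity to Grade 4 and a missing relationship to related. Only Table 14.3.1.1 uses these values, so no table shows which term was affected. With at most 30 subjects, one reclassified subject moves a row by at least 100/30 = 3.3 percentage points.
- Protocol Section 13.3 and SAP Section 1 require the study report to describe departures from the SAP. A summary that the SAP never planned is not such a departure, so its absence may never be explained.

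**Working it through.** No sample size, test or estimate is involved, so the check compares what is promised with what is planned and counts tables. The inputs are Protocol Section 13.3.4, SAP Sections 8.1 to 8.2.2.4, and the table list in SAP Section 9.1.1.

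| SAP table | By SOC/PT | Grade | Relationship, all TEAEs | Relationship, serious TEAEs |
|---|---|---|---|---|
| 14.3.1.1 (overall) | No | Grade 3 or 4 item; death item | One treatment-related item | None |
| 14.3.2.1 (all) | Yes | None | None | None |
| 14.3.2.3.1 (serious) | Yes | None | Not applicable | None |
| 14.3.2.3.2 (non-serious) | Yes | None | None | Not applicable |
| 14.3.2.4 (renal) | Yes | None | None | None |
| 14.3.2.5 (hepatic) | Yes | None | None | None |

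The columns specified for the overall, all, serious and non-serious tables separate the 400 mg BID period, the taper and the total. They do not separate grades or relationship categories.

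Counts:

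- SOC/PT tables that show grade: 0 of 5.
- Tables that show Grade 1 or Grade 2: 0 of 6.
- Tables that give relationship for serious TEAEs, at any level: 0 of 6.
- Tables that give the Grade 3 or 4 proportion (a protocol minimum): 1 of 6, which is enough for that item.
- Tables that give treatment-related TEAEs overall: 1 of 6.

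**Severity.** The protocol names PT, SOC and severity in a single sentence, and the natural reading is a crossed summary. No planned table is one.

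**Relationship.** The protocol sentence covers both AEs and SAEs and does not mention SOC or PT. The treatment-related item in Table 14.3.1.1 arguably satisfies it for TEAEs. Nothing satisfies it for SAEs: that table has a treatment-related item and a serious item, but not the two combined.

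**Can Grades 1 and 2 be recovered?** The overall table gives event counts, so approximately

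Grade 1–2 events = all TEAEs − Grade 3/4 events − fatal events.

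This assumes that each fatal event is outside the Grade 3/4 item. It gives one combined event count, does not separate Grade 1 from Grade 2, and says nothing by term. Since the endpoint is subject incidence, the subtraction does not produce it: a subject can be in both the Grade 3/4 and the death items, and that overlap is not tabulated.

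**Meaning of related.** SAP Section 8 lists five relationship categories but does not say which of them count as treatment-related in Table 14.3.1.1. Protocol Section 12.3 groups possible, probable and definite together, but for expedited reporting.

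**The case against.** The best defence has four parts.

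- **The endpoint is reported.** Neither endpoint statement asks for grade by term, and the protocol's minimum grade item is Grade 3 or 4, which Table 14.3.1.1 provides along with deaths. This stands against any claim that the study fails to report its endpoint. It does not answer the separate severity sentence in the same protocol section.
- **The severity sentence can be read loosely**, as three separate summaries. That is possible but less natural. Even then, a Grade 3/4 item and a death item do not summarize severity across the grades.
- **The SAP discloses reduced output** and supports only an abbreviated report. This mitigates the departure. However, the notice is generic, the SAP keeps graded TEAEs as its endpoint, and it still specifies CTCAE grading, a relationship scale and rules for missing values of both. Nothing in it suggests that these variables were judged irrelevant.
- **The impact is small.** There are at most 30 subjects, no comparator and no hypothesis test, and listings of TEAEs, SAEs, renal and hepatic events are planned. All of this is true: no estimate is biased. The listing columns are not specified, though, and the protocol promises summaries.

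A reader might also infer that the protocol promised related TEAEs by SOC and PT, or grade in the renal and hepatic tables. It promised neither. The relationship sentence names no coding level, and Section 13.3.4 does not call for those renal and hepatic tables.

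**Conclusion.** There is a partial mismatch between protocol and SAP, worth correcting because correction is cheap. Grade is missing from all five SOC/PT tables, Grades 1 and 2 from all six tables, and relationship for serious TEAEs from every table. SAP Section 9 declares none of these as dropped. The severity gap is the firmer part. The relationship gap is confined to serious events.

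It would go too far to conclude that the endpoint is unreported: the Grade 3 or 4 proportion, TEAEs leading to death and treatment-related TEAEs are all tabulated overall.

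The conclusion rests on two assumptions: that the severity sentence means a crossed summary, and that the table list in SAP Section 9.1.1 is complete. On the looser reading of the severity sentence, the Grade 1 and 2 gap and the serious-event gap remain.

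**What to change.** 1. Add a table of TEAEs by SOC, PT and maximum CTCAE grade for the safety population.
2. Add a row for related serious TEAEs to Table 14.3.1.1.
3. State in SAP Section 8.1 that related means possibly, probably or definitely related. Missing relationship is already assigned to related by SAP Section 5.7.2.

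If the sponsor prefers not to produce these, SAP Section 9 should name each dropped summary and give the reason.

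A table of related TEAEs by SOC and PT, and grade in Tables 14.3.2.4 and 14.3.2.5, would help readers but are optional.

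The cost is one standard table, one row and one sentence, all from adverse event variables already collected. The SAP change belongs before database lock. If lock has passed, the same output can be produced as an additional descriptive summary and labelled as such in the report.

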## 14. STUDY ADMINISTRATION

### 14.1. Study Monitoring

Before an investigational site can enter a patient into the study, a representative(s) of BioCryst or its designee will assess the investigational study site to:

- Determine continued adequacy of the facilities
- Discuss with the investigator(s) and other personnel their responsibilities with regard to protocol adherence, and the responsibilities of BioCryst or its designee. This will be documented in a Clinical Study Agreement between BioCryst and the investigator.

During study conduct, BioCryst or its designee will conduct periodic monitoring visits to ensure that the protocol and Good Clinical Practice (GCP) are being followed. The monitor(s) will review source documents to confirm that the data recorded on eCRFs are accurate. The investigator and institution will allow the representative(s) of BioCryst or its designee access to source documents to perform this verification.

It is important that the investigator(s) and relevant personnel are available during the monitoring visits and that sufficient time is devoted to the process.

During the study, a representative(s) from BioCryst or its designee will have regular contacts with the investigational site personnel for the following:

- Provide information and support to the investigator(s)
- Confirm that facilities remain acceptable

- Confirm that the investigational team is adhering to the protocol, that data are being accurately recorded in the eCRFs, and that IMP accountability checks are being performed
- Perform source data verification. This includes a comparison of the data in the eCRFs with the subject's medical records at the hospital or practice, and other records relevant to the study. This will require direct access to all original records for each subject (eg, clinic charts).
- Record and report any protocol deviations not previously sent to BioCryst or its designee
- Confirm AEs and SAEs have been properly documented on the eCRFs and confirm any SAEs have been forwarded to BioCryst or its designee and those SAEs that met criteria for reporting have been forwarded to the ethics committee

The representative(s) of BioCryst or its designee will be available between visits if the investigator(s) or other staff needs information or advice.

## **14.2. Audits and Inspections**

Authorized representatives of BioCryst or its designee, US FDA and other regulatory authorities, and/or ethics committee may visit the site to perform audits or inspections, including source data verification. The purpose of a BioCryst audit or inspection is to systematically and independently examine all study-related activities and documents to determine whether these activities were conducted, and data were recorded, analyzed, and accurately reported according to the protocol, standard operating procedures, ICH GCP guidelines, and any applicable regulatory requirements. The investigator should contact BioCryst immediately if contacted by a regulatory agency about an inspection.

It is important that the investigator and relevant personnel are available during the possible audits or inspections and that sufficient time is devoted to the process.

## **14.3. Ethics Committee**

The investigator must obtain ethics approval for the investigation. Initial ethics approval and all materials approved by the ethics committee, including the ICF and any recruitment materials, must be maintained by the investigator and made available for inspection.

## **14.4. Serious Breaches of GCP**

It is the responsibility of the sponsor to notify the competent authority of any serious breach of GCP that is likely to affect, to a significant degree, the safety or mental integrity of the subjects of the study or the scientific value of the study. All serious breaches will be notified to the relevant competent authority in accordance with locally applicable regulations. The reporting to the sponsor will be performed by the party who suspects the serious breach.

# **15. QUALITY CONTROL AND QUALITY ASSURANCE**

During study conduct, BioCryst or its designee will conduct periodic monitoring visits to ensure that the protocol and GCPs are being followed as described in Section [14.1](#).

To ensure compliance with GCP and all applicable regulatory requirements, BioCryst or its designee may conduct a quality assurance audit. Please see Section [14.2](#) for more details

regarding the audit process. The investigator agrees to allow the auditors to inspect the drug storage area, study drug stocks, drug accountability records, subject charts and study source documents, and other records relative to study conduct.

